**Table 2: Visit Windows of Group A/B**

Analysis Phase	Scheduled Visit Number	Time Interval (label on output)	Time Interval (Day)*	Target Time Point (Day)
Screening phase	1	Screening	<1	[-56,0]
Investigation phase	2	Baseline	1	1
	3	Week 2	[2,22]	15
	4	Week 4	[23,36]	29
	5	Week 6	[37,50]	43
	6	Week 8	[51,64]	57

Analysis Phase	Scheduled Visit Number	Time Interval (label on output)	Time Interval (Day)*	Target Time Point (Day)
	7	Week 10	[65,78]	71
	8	Week 12	[79,99]	85
	9	Week 16	[100,127]	113
	10	Week 20	[128,156]	141
	11	Week 24	[157,184]	169
	12	Week 28	[185,212]	197
	13	Week 32	[213,240]	225
	14	Week 36	[241,268]	253
	15	Week 40	[269,296]	281
	16	Week 44	[297,324]	309
Follow-up phase (Group A)/ Investigation phase (Group B)	17	Week 48	[325,352]	337
	18	Week 52	[353,380]	365
	19	Week 56	[381,406]	393
	20	Week 60	[407,425]	421

\*Relative to the date of starting dose in investigation phase

**Table 3: Visit Windows of the Optional Cohort**

Analysis Phase	Scheduled Visit Number	Time Interval (label on output)	Time Interval (Day)*	Target Time Point (Day)
Optional Investigation phase	2	Optional Baseline	1	1
	3	Optional Week 2	[2,22]	15
	4	Optional Week 4	[23,36]	29
	5	Optional Week 6	[37,50]	43
	6	Optional Week 8	[51,64]	57
	7	Optional Week 10	[65,78]	71
	8	Optional Week 12	[79,99]	85
	9	Optional Week 16	[100,127]	113
	10	Optional Week 20	[128,156]	141
	11	Optional Week 24	[157,184]	169
	12	Optional Week 28	[185,212]	197
	13	Optional Week 32	[213,240]	225
	14	Optional Week 36	[241,268]	253
	15	Optional Week 40	[269,296]	281
	16	Optional Week 44	[297,324]	309
	17	Optional Week 48	[325,352]	337

\*Relative to the date of starting dose in optional investigation phase

## 5.2. Participant Dispositions

The number of participants in the following disposition categories will be summarized throughout the study by intervention group and overall:

- Participants randomized
- Participants who received study intervention
- Participants who completed the study
- Participants who discontinued study intervention
- Participants who discontinued study
- Participants who switched to the optional cohort

- Participants who switched to the individualized treatment regimen
- Reasons for discontinuation of study intervention
- Reasons for discontinuation of study

Listings of participants (eg, the date of last study visit, the last study phase and week, the date of discontinuation and the reason) will be provided for the following categories:

- Participants who discontinued study intervention
- Participants who discontinued study
- Participants who were randomized yet did not receive any study interventions.

### **5.3. Primary Endpoint Analysis**

#### **5.3.1. Definition of Endpoint**

The primary endpoint of this study is Sputum Culture Conversion in MGIT at Week 24. Sputum culture conversion is defined as 3 consecutive negative sputum cultures taken at least 25 days apart based on actual collection dates. Sputum cultures at unscheduled visits will also be used for the determination of sputum culture conversion.

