## Footnotes:

- a. Screening evaluations must be performed within 70 days (10 weeks) prior to baseline (Day 1). These 10 weeks include 14 days of rifamycin W/O for participants to whom it is applicable. If screening period exceeds 10 weeks for reasons such as time required to obtain the result of microbiology assessment of screening, the screening period may be extended up to 15 weeks.
- b. If required during the 48-week treatment period, participants can have a change in their treatment regimen, in which MAC-LD treatment may continue in accordance with standard of care or NTM treatment guidelines. All decisions on treatment regimen change should be made based on clinical worsening supported by microbiology data by the investigator. Participants requiring a treatment regimen change will be followed up for safety only, but all assessments should be performed according to the protocol.
- c. Assessments planned on Day 1 except for blood sampling for PK which is performed after dosing must generally be performed prior to first dose of study intervention.
- d. Every 4-week visit must be scheduled after more than 25 days from the previous visit.
- e. The participants who have been treated with BDQ-containing regimen (Group A) through Week 48 and culture converted, will transfer to the follow-up period. The participants who have been treated with rifamycin-containing regimen (Group B) through Week 48 will continue to be treated up to Week 60.
- f. Early discontinuation visit is to be scheduled within 7 days of the investigator's discretion to discontinue treatment with study intervention (including the day of discontinuation, other than withdrawal of consent). Visit for switch to individualized treatment regimen is to be scheduled within 7 days after discontinuing the assigned treatment regimen (including the day of switch) and before the start of individualized treatment regimen.
- g. Must be signed before first study-related activity.
- h. Investigators should ensure that all study enrollment criteria have been met at screening. If a participant's clinical status changes (including any available laboratory results or receipt of additional medical records) after screening but before the first dose of study intervention is given such that he or she no longer meets all eligibility criteria, then the participant should be excluded from participation in the study.
- i. Medical and surgical history, including NTM exposure history, NTM treatment history, and MAC-LD.

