- j.  $\beta$ -hCG test will be performed only at screening and Day 1 whereas urine pregnancy test at timepoints described in SoA other than screening and Day 1.
- k. FSH test is performed only for postmenopausal women.
- l. After Week 48, only participants in Group B will continue to administer study intervention, and study intervention accountability will be continued up to Week 60.
- m. Two sputum samples should be collected at each visit time point except for Week 2, 6, and 10. One should be collected in the early morning at home and the other sample(s) at the study site. If sputum collection at home is impossible, 2 samples will be collected at the study site. If sputum can be produced more easily in the evening/night than in the early morning, it is acceptable to store the sample obtained in the previous day of visit in a refrigerator, bring it to the study site, and submit it on the following day. Samples collected at home or the study site can be spontaneous, induced or aspirated. In case 2 sputum sample collection is not feasible at Week 2, 6, and 10, either no sample or 1 sample collection is allowed. Sputum samples will be shipped to the central microbiology laboratory where all cultures will be performed on solid and on liquid media. The same applies to sputum collections at OPW 2, 6 and 10 in the optional cohort. And in case a sputum sample is collected in routine clinical practice before obtaining informed consent on the day of informed consent, it is acceptable to submit as a sputum sample for the study after obtaining the participant's consent and recorded.
- n. Identification and speciation of MAC will be done by MALDI-TOF MS at screening, baseline, and postbaseline for all positive sputum culture(s)
- o. BACTEC MGIT™ will be used for qualitative culturing in an automated mycobacterial detection system.
- p. Drug susceptibility testing (DST) will be done on culture positive isolates at screening, baseline, and at Week 24. The testing will be done on the last culture positive isolates in case of participants with non-conversion and recurrence (relapse/reinfection). In addition, the testing will be done on positive isolates at early discontinuation (if available). In the optional cohort, DST will be done on the last culture positive isolates in case of participants with non-conversion and recurrence (relapse/reinfection), as well as positive isolates at early discontinuation (if available).

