### 5.1. Inclusion Criteria

Each potential participant must satisfy all of the following criteria to be enrolled in the study:

1. Male or female.
2. 20 to 79 years of age, inclusive.
3. Has body weight  $\geq 40$  kg at screening and on Day 1.
4. Has radiological evidence consistent with NTM-LD based on a chest CT scan taken within 6 months prior to screening or at screening.
5. Criterion modified per Amendment 4.
- 5.1 Criterion modified per Amendment 8.
- 5.2 Has at least 2 positive sputum cultures of MAC (sputum cultures to be taken at least 4 weeks apart):

- one obtained within 12 months prior to screening, which was documented while being treated for MAC-LD for a total of at least 6 months.
  - one at screening (by central microbiology laboratory).
6. Criterion modified per Amendment 4.
- 6.1 Criterion modified per Amendment 8.
- 6.2 Received at least 6 months of consecutive MAC-LD treatment (at least 2 antibiotics for MAC, including a macrolide), that is either ongoing or has stopped within 12 months prior to screening.
- Note: Participants must be compliant with medication intake for at least 75% of the total doses for prescribed SOC (including intermittent regimen) recommended by local guidelines. Participants who have missed more than 25% of their doses during a given treatment period for any reason (including noncompliance by participants, interruption due to an AE at the discretion of physician, and others) can only be enrolled if approved by the sponsor's medical monitor.
7. No presence of cognitive dysfunction that would impact the completion of the patient-reported outcome (PRO) assessments.
8. Must sign an informed consent form (ICF) indicating that he or she understands the purpose of, and procedures required for, the study and is willing to participate in the study.
9. A woman of childbearing potential must have a negative highly sensitive serum ( $\beta$ -human chorionic gonadotropin [ $\beta$ -hCG]) test at screening and on Day 1.
10. A woman using oral contraceptives must use an additional contraceptive method (as required in Inclusion Criterion 11).
11. A woman must be (as defined in Section 10.5, [Appendix 5: Contraceptive Guidance](#)).
- a. Not of childbearing potential
  - b. Of childbearing potential and

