## **5.4. Screen Failures**

### **Participant Identification, Enrollment, and Screening Logs**

The investigator agrees to complete a participant identification and enrollment log to permit easy identification of each participant during and after the study. This document will be reviewed by the sponsor study-site contact for completeness.

The participant identification and enrollment log will be treated as confidential and will be filed by the investigator in the study file. To ensure participant confidentiality, no copy will be made. All reports and communications relating to the study will identify participants by participant identification and age at initial informed consent. In cases where the participant is not randomized into the study, the date seen and age at initial informed consent will be used.

Individuals who do not meet the criteria for participation in this study (screen failure) may be rescreened, including candidates whose microbiological testing at screening is not eligible, such as culture negative, resistance to CAM, etc. Rescreened participants should be assigned a different participant number with the initial screening.

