### Data Included

All randomized participants who take at least 1 dose of study intervention will be used.

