### **5.4.2. Supportive Secondary Endpoints**

#### **5.4.2.1. Definition of Endpoints**

##### **Sputum culture conversion in MGIT and 7H10 or 7H11 agar media**

The definition of sputum culture conversion is described in Section 5.3.1.

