## **6.2. Appendix 2 Changes to Protocol-Planned Analyses**

The per-protocol analysis set defined in the protocol will not be used for analysis.

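### Culture conversion needs no pre-dose positive in the same medium, so participants negative in that medium before dosing can count as converters, and no planned analysis separates them

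*SAP*

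**What the plan says.** **Endpoint.** SAP 5.3.1: "Sputum culture conversion is defined as 3 consecutive negative sputum cultures taken at least 25 days apart based on actual collection dates". Cultures from unscheduled visits also count. For the secondary conversion endpoints in MGIT and agar, SAP 5.4.2.1 adds nothing: "The definition of sputum culture conversion is described in Section 5.3.1".

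**Entry.** Protocol 5.1, criterion 5.2, asks for at least two MAC-positive sputum cultures at least 4 weeks apart. One comes from the 12 months before screening, documented on treatment. The other is described as "one at screening (by central microbiology laboratory"). No medium is named, although footnote m of the Schedule of Activities says "all cultures will be performed on solid and on liquid media".

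**Timing.** Screening lasts up to 10 weeks. Under footnote a, if for example the screening culture result is late, "the screening period may be extended up to 15 weeks". Under Protocol 5.4, screen failures "may be rescreened, including candidates whose microbiological testing at screening is not eligible, such as culture negative". Sputum is also cultured on Day 1, but no rule uses that result to define conversion.

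**Analysis.** For the main estimator, SAP 5.3.2.1 says: "All randomized participants who take at least 1 dose of study intervention will be used". The sensitivity estimator (SAP 5.3.2.2) changes only the stratifier, to MAC type. Subgroups (SAP 5.3.4) are the categorical variables of Tables 7 and 8, and pre-dose culture status is not among them. SAP Appendix 2 adds: "The per-protocol analysis set defined in the protocol will not be used for analysis".

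**The concern.** Conversion means going from positive to negative, but the definition tests only the second half. Two kinds of participant meet it without any change during the trial:

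- **Agar.** The screening positive may have come from MGIT alone. If the participant never grows MAC on agar, three agar negatives follow by default.
- **MGIT, the primary endpoint.** A participant with a positive screening culture may already be MGIT-negative on Day 1, weeks later. If they stay negative, they are a Week 24 converter in whichever arm they were assigned.

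If these participants stay negative about equally often in both arms, they raise both conversion rates and shrink the difference between them. The agar endpoint is the more exposed, because no entry rule requires agar growth at any time. The primary endpoint is exposed only through the interval between the screening culture and Day 1, or through a screening culture positive on agar alone.

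**Working it through.** **Step 1: the plan's own figure.** Inputs from SAP section 3 and Protocol 9.2: control rate 10%, difference 20 points (so 30% in Group A), 62 per arm, two-sided 5% chi-square test. Using the pooled-variance normal approximation without continuity correction, with p̄ the mean of the two rates,

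power = Φ{ [Δ − 1.96·√(2p̄(1−p̄)/n)] / √([pA(1−pA) + pB(1−pB)]/n) }.

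With p̄ = 0.20 and n = 62: (0.20 − 0.1408)/0.0696 = 0.851, so power is 80.3%. The required size is 62 per arm, 124 in all. The plan's figure is reproduced.

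**Step 2: a dilution model.** Let f be the share of each arm that is negative in the medium before dosing, and q the probability that such a participant is counted as a converter, the same in both arms. Let 10% and 30% be the rates among baseline-positive participants. Then

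- pB = f·q + (1−f)·0.10
- pA = f·q + (1−f)·0.30
- difference = (1−f)·0.20

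The documents give neither f nor q, so the values below are assumptions.

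| f | q | pB | pA | difference | power, 62 per arm |
|---|---|---|---|---|---|
| 0 | – | 10.0% | 30.0% | 20.0 points | 80.3% |
| 5% | 0.5 | 12.0% | 31.0% | 19.0 points | 73.6% |
| 5% | 1.0 | 14.5% | 33.5% | 19.0 points | 70.2% |
| 10% | 0.5 | 14.0% | 32.0% | 18.0 points | 66.7% |
| 10% | 1.0 | 19.0% | 37.0% | 18.0 points | 60.9% |

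Most of the loss comes from the higher rates in both arms rather than from the smaller difference. At f = 10%, counting these participants as non-converters (9% v 27%, still 18 points) would leave power at 74.8%.

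**Step 3: the assumption of no treatment effect.** Take f = 20%, and suppose 80% of baseline-negative participants in Group A and 60% in Group B are counted as converters. The rates are 0.8·0.30 + 0.2·0.80 = 40% and 0.8·0.10 + 0.2·0.60 = 20%. The difference stays at 20 points and power is about 69%. With 50% v 30% instead, the rates are 34% v 14% and power is about 75%. The difference shrinks only if treatment does less in these participants than in the others.

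**Step 4: what a restricted analysis costs.** Leaving baseline-negative participants out gives 62(1−f) per arm at 10% v 30%. Power is 78.2% at f = 5% (58.9 per arm) and 75.9% at f = 10% (55.8 per arm).

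**The case against.** The case on the other side is substantial.

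- **Entry is stricter than the endpoint definition alone suggests.** Two documented MAC positives are required, and a rescreened candidate signs a new consent form and still needs a central-laboratory positive. This stands and limits how many participants can be affected. A reader might infer that candidates can be retested without limit until one culture is positive. The protocol states no limit, but silence is weak support for that reading.
- **Day 1 as the first of the three negatives.** A reader might infer that a Day 1 sample can help decide Week 24 status. The SAP does not expressly bar it, but the documents point the other way. Protocol 4.2 describes negatives collected during treatment, Protocol 9.4.4 calculates conversion percentages after Week 4, and SAP Table 4 judges Week 24 from Weeks 8 to 24. The point does not need this reading: a participant who stays negative has enough later negatives.
- **The 10% may already include such participants.** It comes from two trials in a population described as analogous. If those trials counted conversion in the same way, planned power stands. The documents do not settle this.
- **Three negatives are hard to reach by chance.** Two samples are planned at most visits, so q could be low in an intermittent shedder. This stands as a reason not to rely on the upper end of the range.
- **Some information would appear anyway.** MGIT time to positivity is summarised by visit among positives (SAP 5.4.2.2.5), so baseline MGIT positivity might be visible there. It would not be linked to conversion and would not cover agar.
- **Agar is only supportive.** True: SAP 5.4.1 names no key confirmatory secondary endpoint.

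**Conclusion.** The gap is real. Followed exactly, the plan counts a never-agar-positive participant as an agar converter, and a Day 1 MGIT-negative participant who stays negative as a primary converter, unless an intercurrent event makes them a non-converter. No planned analysis set, sensitivity estimate or subgroup separates them.

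The consequence is a possible loss of power and a smaller observed difference. Randomisation balances these participants in expectation, so neither type I error inflation nor bias in favour of bedaquiline follows.

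The size is unknown. The figure of 61–74% against 80% is an illustration. It rests on a baseline-negative share of 5–10%, on 50–100% of those participants being counted as converters, on no treatment effect in them, and on 10% and 30% being rates among baseline-positive participants. A reader might infer that the bedaquiline effect is shown to be diluted, or that power falls much further under larger shares. The documents support neither, because they report no baseline-negative share.

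This is an inexpensive improvement to what the agar endpoint measures and to how the primary result can be interpreted. It is not a flaw in the validity of the primary test.

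**What to change.** 1. **SAP 5.4.2.2.1.** Analyse agar conversion in ITT participants with at least one MAC-positive agar culture at screening or Day 1, and report the number excluded in each arm.
2. **SAP 5.3.2.2 and Table 8.** Keep the ITT primary analysis unchanged. Add one sensitivity estimate restricted to participants MGIT-positive on Day 1, and add Day 1 MGIT status (positive or negative) to Table 8 as a subgroup variable. A condition on Day 1 is needed because a screening positive would not identify someone who turned negative before dosing. State how a missing or contaminated Day 1 culture is classified.
3. **SAP 5.3.1.** As a minor alignment with Protocol 4.2, state that the three negatives are collected after the first dose.

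The cost is SAP wording and a small amount of extra output. Screening and Day 1 cultures are already collected in both media. Because they are taken before dosing, the restrictions keep the randomised comparison. The downside is a slightly smaller set for the agar endpoint and for the sensitivity estimate. The changes show the effect of any dilution but do not restore power for the primary test. They should be settled before microbiology results are unblinded for the primary analysis.

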#### **5.3.2. Primary Estimand**

The main clinical quantity of interest to be estimated in this study, is defined by the following 5 components:

- Population: Adult patients with treatment-refractory MAC-LD
- Endpoint: Proportion of participants with sputum culture conversion (sputum culture conversion rate) in MGIT at Week 24.
- Treatment: BDQ-containing regimen versus rifamycin-containing regimen.
- Population Level Summary: The difference of proportions between treatment groups.
- Intercurrent Events (ICE):
  - a. Deaths, treatment discontinuation and treatment regimen changes prior to Week 24: all these ICEs will be handled by a composite strategy to treat the participants as nonconverters.
  - b. Major protocol deviations (besides treatment regimen changes prior to Week 24): all data will be used regardless of the occurrence of major protocol deviations (treatment policy strategy).

##### **5.3.2.1. Main Estimator of the Primary Estimand**

#### **Assumptions**

- Missing not at random: missing data due to deaths, treatment discontinuation and treatment regimen changes will be treated as nonconversion.

- No prognostic factors for the proportion of converters.

### Data Included

All randomized participants who take at least 1 dose of study intervention will be used.

### Missing Data Handling Rule

A contaminated or missing sputum culture occurring between two negative cultures will be interpreted as “no data” and will not contribute to the assessment of the 3 consecutive negative cultures.

Table 4 shows how to judge the response at Week 24 with considering missing samples or contaminated sputum cultures.

**Table 4: Cases of Sputum Culture Conversion**

Week 8	Week 10	Week 12	Week16	Week 20	Week 24	Converter?
Neg/Pos	Neg/Pos	Neg	Missing	Neg	Neg	Yes
Neg/Pos	Neg/Pos	Neg	Neg	Missing	Neg	Yes
Neg/Pos	Neg/Pos	Neg	Neg	Neg	Missing	Yes
Neg	Neg	Neg	Missing	Missing	Neg	Yes
Pos	Neg	Neg	Missing	Missing	Neg	No
Neg	Pos	Neg	Missing	Missing	Neg	No

\*Missing includes the missing samples and contaminated sputum culture.

### Analysis Methods

Cochran-Mantel-Haenszel test stratified by region (Japan, non-Japan) at the 5% 2-sided significance level will be used to compare sputum culture conversion rate in MGIT at Week 24. The proportion of the participants with sputum culture conversion at Week 24 will be summarized as randomized and the stratum adjusted treatment difference with 2-sided 95% CI will also be presented.

#### 5.3.2.2. Sensitivity Estimator of the Primary Estimand

##### Assumptions

- Missing not at random: missing data due to deaths, treatment discontinuation and treatment regimen changes will be treated as nonconversion.
- The type of MAC (*M. avium*, *M. intracellulare* and *M. avium* + *M. intracellulare*) is a possible prognostic factor for the proportion of converters.

